7 POTENTIAL BENEFITS

There may or may not be any benefit to participating in this study. This technique is still being investigated. It may provide some therapeutic value for subjects with few or no other options due to the great risk that would be involved in open resection. The symptoms may decrease and/or the quality of life of the subject may improve due to relief of symptoms. However, there is no guarantee that this procedure will reduce, eliminate symptoms, or otherwise treat the underlying disorder. Other subjects may benefit from this procedure in the future, if further trials prove it to be a safe and effective therapy.

8 MONITORING PLAN

Clinical Monitoring for this study will be managed by InSightec. The Clinical Monitor is qualified by training and experience to oversee the conduct of this study. The Clinical Monitor's responsibilities include maintaining regular contact with each investigational site through telephone contact and on-site visits, to ensure that:

- The trial is conducted according to FDA and GCP requirements;
- The trial is conducted according to InSightec internal SOPs
- The Investigational Plan is followed;
- Complete, timely, and accurate data are submitted;
- Problems with inconsistent or incomplete data are addressed;
- Complications and unanticipated adverse effects are reported to the Sponsor and the IRB;
- The site facilities will be monitored to stay adequate to meet the requirements of the study.

The Clinical Monitor will initiate the Study during an on-site visit and will continue to perform on-site monitoring visits as frequently as deemed necessary. The first monitoring visit will usually be made as soon as possible after enrollment has been initiated. At this visit and all monitoring visits, the Clinical Monitor will compare the data entered onto the

CRFs with the hospital or clinical records (source documents). Source documentation must be available to substantiate proper informed consent procedures, adherence to protocol procedures, adequate reporting and follow-up of AEs, and device procedure information. Findings from the review of CRFs and source documents during a monitoring visit will be discussed with the PI. Completed paper or electronic CRFs will be reviewed prior to data closure at each visit. The dates of the monitoring visits will be recorded in a Log to be kept at the clinical site. During monitoring visits, the Sponsor expects that the study coordinator and the PI will be available, the source documentation will be available, and a suitable environment will be provided for review of Study related documents.

Sites should make every effort to contact all subjects for study follow-up to encourage visit compliance. Sites should keep a log of dates of attempted contact and results. After 3 unsuccessful attempts at contact (e.g., by telephone or email) and sending 1 certified letter to solicit their visit compliance a subject may be considered lost to follow-up.

Monitoring procedures will follow the Sponsor SOPs.

8.1 Electronic Data Capture (EDC)

Electronic CRFs (eCRFs) will be to capture protocol-specific information during the conduct of this study. This electronic data capture of the eCRFs is based on the Oracle Software system, and is designed, run and hosted by Sponsor (Haifa, Israel).

9 INVESTIGATOR RESPONSIBILITIES

The Principal Investigator will be required to sign the Investigator Agreement. All investigators will undergo extensive training on the protocol and operation of the ExAblate system, and provide documentation of their specialized training.

11.1 Movement Disorder in Essential Disorders Patients

Essential tremor is the most common movement disorder with an estimated prevalence between 0.3% and 5.6% [1-5]. Recent epidemiological reports⁴ indicate that prevalence across 19 countries (pooled) was 0.9%, but increased to 4.6% among those 65 years and as high as 21.7% in those aged 95 and older. The condition is a genetically inherited disorder with a child of an ET person having a 50% chance of inheriting a gene causing the condition. Approximately 50-70% of people diagnosed with ET have a positive family history for the condition. Caucasians are 5 times more likely to report physician diagnoses of ET than are African Americans; Hispanics have a rate between them. Gender predisposition as reported in various articles is variable depending upon the author's population.

ET is a slowly progressive neurological disorder characterized by a tremor of the arms or hands that occurs during voluntary movements (intention tremor), such as eating/drinking and writing. The tremor may also present in the head (neck) and jaw and may affect voice. The disease may present in the teens or in the 40-50 age range. Generally, tremor begins in the arms and then spreads to these other regions in selected patients. Other types of tremor may also present, including postural tremor of the outstretched arms, and intentional tremor (below 5 Hz) and rest tremor of the arms. The amplitude of an intention tremor increases as an extremity approaches the endpoint of deliberate and visually guided movement (hence the name intention tremor). An intention tremor is usually perpendicular to the direction of movement. An intention tremor causes the person to overshoot or undershoot their target (dysmetria).

11.2 ExAblate Neuro System.

The non-invasive high-intensity focused ultrasound has been coupled with high resolution MRI to provide precise, consistent treatments that can be monitored in real-time. The development of phased array transducers allows for tightly focused treatment volumes and for the ability to compensate for distortions by tissue heterogeneity [6-8]. The landmark advance in the ExAblate transcranial MR guided focused ultrasound for neurosurgeons occurred as the ability to sonicate through the intact cranium was achieved with phased array transducers and acoustic modeling using CT reconstructions of the skull [6-10]. By coupling focused ultrasound technology with MRI, the ExAblate system allows detailed treatment plans to be performed and real time intra-procedure monitoring [11]. Standard MR sequences have been shown to reliably predict tissue damage during thermal lesioning with ultrasound [11, 12]. We anticipate that the ExAblate Neuro non-invasive thermal lesioning is safe and will provide several years of benefit through reduction of contralateral motor symptoms and potential medication side effects in ET subjects.

⁴ http://www.medmerits.com/index.php/article/epidemiology_of_movement_disorders/P4

12 OBJECTIVES

The objective of this clinical trial is to follow, observationally, the medication-refractory Essential Tremor subjects who underwent ExAblate Neuro thalamotomy under IDE# G120246 to capture long-term safety and effectiveness out to Year 5.

Safety: To evaluate long-term incidence and severity of adverse events (AE/AEs) associated with ExAblate Neuro treatment of medication-refractory ET

Effectiveness: To collect long term effectiveness and quality of life of the ExAblate Neuro treatment of medication-refractory Essential Tremor (ET).

This study is designed as a long-term prospective, observational clinical trial to follow device related safety, and long term effectiveness (CRST) and quality of life (QUEST) for subjects previously treated with ExAblate Neuro under IDE#120246.

The purpose of this protocol is to set the follow-up schedule for all IDE #G120246 subjects out to Year 5 in compliance with the post approval conditions.

12.1 Primary Endpoints

12.1.1 Safety

Safety of ExAblate will be determined by an evaluation of the incidence and severity of device / treatment related complications from the treatment day visit through ALL study follow ups through Year 5. Adverse events (type, frequency, severity) are expected to be similar to those of previous studies using ExAblate Neuro for Thalamotomy

Recorded adverse events will be reported and categorized by investigators as definitely, probably, possibly, or unrelated to the device or procedure. Events which are not considered to be possibly or probably caused by the device are not required to be reported here.

12.1.2 Effectiveness

Primary effectiveness will be assessed using the CRST as scored by the site neurologist.

Secondary effectiveness will be followed using the QUEST quality of life patient outcomes questionnaire.

12.1.2.1 Efficacy Assessments

Tremor symptom severity will be assessed using the CRST as scored by the site neurologist at each follow-up visit. The CRST is a validated clinical instrument used to assess tremor symptom severity.

Quality of life will be evaluated using the QUEST assessment to assess durability (as measured by QUEST upper arm extremity questions) of the procedure. The QUEST is an ET specific assessment of quality of life changes associated with ET. Tröster *et al.*, 2005, developed QUEST as a clinical tool for correlating changes in 30 aspects of tremor

severity, social and personal disability, and perception of health. An independent validation study of the QUEST performed by Martinez-Martin *et al.* concluded that most of the psychometric parameters were found to be satisfactory in their ability to assess the impact of ET on the patients' quality of life.

12.2 Study Hypothesis

The purpose of this study is to continue to follow the ExAblate-treated medication-refractory ET subjects for long-term safety and effectiveness of MRI-guided focused ultrasound thalamotomy out through 5 years.

12.3 Case Report Form Data

The study data will be collected electronically. This electronic data capture (EDC) system complies with the current guidance of 21 CFR Part 11, Electronic Records and Signatures.

13 DESCRIPTION OF PATIENT POPULATION

13.1 Patient Selection

13.1.1 Inclusion Criteria

13. Subjects who have been treated with ExAblate thalamotomy for medication-refractory ET under previous clinical trials.

13.1.2 Exclusion Criteria

1. Subjects who have had a subsequent intervention for ET on their treated side.

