4.2.2.3.2 Reasons for Study Exit

In this study, subjects who opt for alternative treatments for Essential Tremor (not including medication change) at any point in the follow-up period will be exited from the study after completing required study examinations. The last set of evaluations prior to alternative therapy is considered the last study visit. The reason(s) for study exit will be noted on the Case Report Forms. No analyses of post alternative treatment changes are planned.

4.2.2.4 Month 6 and 12

To assess treatment long term safety and efficacy durability (i.e.: study secondary endpoint), follow up will also be completed at the 6 and 12 months post treatment. At these visits, all the data will be collected in the same fashion with videotaped tremor assessments as during the other visits, except that subjects and site assessor may no longer be blinded. These 6/12-Months videotapes must also be forwarded to the sponsor for storage.

The following evaluations should be performed at Month 6 and 12:

- Review of medications
- Physical exam
- Neurological status
- CRST (SBA unblinded) with videotaping,
- QUEST and PHQ-9-depression questionnaires should be completed by the subject
 - NOTE:

At any follow up visit, any subject who scores ≥ 20 on the PHQ-9 questionnaire, the subject should be referred out for psychiatric evaluation. The Columbia Suicide Severity Rating Scale, or like, may be used. Should there be a psychiatric treatment, then this psychiatric treatment should be recorded as an adverse event. A Copy of the psychiatric evaluation should become part of the CRF information as part of the adverse event outcomes and description. The investigator will evaluate whether the subject may continue participation in the study, or should be exited from the study for treatment

- Adverse events
- At Month 12 (ONLY), all subjects should undergo the following MR exams:
 - T2 weighted imaging

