14.2 Exit from the study for reason of alternative treatment

In this study, subjects who opt for alternative treatments for Essential Tremor (not including medication change) at any point in the follow-up period will be exited from the study after completing the required study examinations. The last set of evaluations prior to alternative therapy is considered the last study visit. The reason(s) for study exit will be noted on the Case Report Forms. No analyses of post alternative treatment changes are planned.

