14.3 Study Requirements and Visit Schedule

All subjects who were part of the original IDE, IDE # G120246 in either the ET002 pivotal trial, or the ET002CA (Note: inclusive of all patients treated under the original Pivotal Study, those treated under the Continued Access approval, and those treated as part of the 1.5T Coil cohort) will be rolled into this PAS study at whatever stage of follow-up is coming due. Follow-up will be continuous from the time of treatment to the Year 5 visit.

Subjects who have not attained Month 12 will continue their schedule of visits as (originally scheduled):

- 1 Week \pm 3 days
- 1 Month \pm 7 days,
- 3 Month \pm 14 days
- 6 Months \pm 21 days
- 12 Months \pm 4 month

| Table 4.2.2.3.2—1 | | | | | | | | | |
|---|-----------|----------|-----------|-------|--------|---------|---------|---------|----------|
| Summary of Study Schedules and Measurements | | | | | | | | | |
| | Screening | Baseline | Treatment | 1 Day | 1 Week | 1 Month | 3 Month | 6 Month | 12 Month |
| Consent | X | | | | | | | | |
| Eligibility Evaluation with labs | X | X | | | | | | | |
| Medications | X | X | X | X | X | X | X | X | X |
| 30 day meds stabilization | | X | | | | | | | |
| Medical History | X | | | | | | | | |
| Physical Exam | X | X | | X | X | X | X | X | X |
| Neurological status | X | | X | X | X | X | X | X | X |
| CRST | X | | | | | X | X | X | X |
| QOL (QUEST) | X | X | | | | X | X | X | X |
| PHQ-9 | X | | | | | X | X | X | X |
| CT | X | | | | | | | | |
| MR | | X | X | | | | | | X |
| Treatment | | | X | | | | | | |
| Adverse Events | | | X | X | X | X | X | X | X |
| Forms “UB-04 (In Patient subjects) or CMS-1500 (Out Patient subjects) | | X | X | X | X | X | X | X | X |
| Exit Form | | | | | | | | | X |

The table below summarizes the long-term study visit schedule and procedures.

The study visits are as follows:

Year 2 ± 4 Month;

Year 3 ± 4 Month,

Year 4 ± 4 Month,

Year 5 ± 4 Month.

Table 4.2—2 Summary of Study Schedules and Evaluations

| | Year 2 4 Month | Year 3 \pm 4 Month | Year 4 \pm 4 Month | Year 5 \pm 4 Month |
|-----------------------|---------------------------|--|--|--|
| Physical Exam | X | X | X | X |
| CRST | X | X | X | X |
| QOL (QUEST) | X | X | X | X |
| ET medications | X | X | X | X |
| Adverse Events | X | X | X | X |
| Exit Form | X | X | X | X |

Note:

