15.5 Statistical Considerations and Sample Size

There is no statistical consideration or sample size for this study. All ExAblate treated subjects who were treated under ET002 or ET002-CA will be included in this study, starting at the next scheduled study visit date; ET002-CA was FDA approved under IDE Supplement G120246/S07.

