15.8 Subject Confidentiality

Subject confidentiality will be maintained throughout this study, including all publications. Data collected and entered into the CRFs are the property of the study sponsor. Representatives from the study sponsor or authorized sponsor representatives, the Institutional Review Board, Data Safety Monitoring Board, Ethics Committee or other regulatory bodies may receive copies of the study records and may review medical records related to the study.

16 PMA P150038 Specific Questions

What serious or unexpected adverse events may occur in the long-term (up to 5 years) after receiving treatment for the proposed indication?

No known device-related SAEs/UADEs are expected over the follow-up of subjects through Year 5 based on historical literature on thalamotomies as published in the literature. The ExAblate procedure is a one-time procedure. However, per this study protocol, safety data will be collected through Year-5 as planned. The full safety data will be reported to the Agency as required.

In the long-term (5 years), will favorable Composite Tremor/Motor Function scores compared to the baseline be sustainable among the patients who have received the treatment?

Based on historical outcomes as published in the literature, it is reasonable to believe that the Composite Tremor/Motor Function improvement will be maintained through follow-up. However, because this cohort of subjects is the first group of subjects to be treated using the ExAblate 4000 device and for many investigators, this was the first hands-on experience in using the device, it is reasonable to anticipate that there may be some patients who do not sustain their improvement over the duration of this study. With the accumulation of user expertise in using the ExAblate 4000, it is expected that the composite Tremor/Motor score outcomes will be sustainable over long durations. It is the purpose of this long-term follow-up protocol to capture the very long term data of the composite Tremor/Motor scores for this cohort of subjects.

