17.1 Criteria for Removal from the Study

The investigator may withdraw subjects from the study as is deemed necessary or deemed to be in the best interests of the subject, such as,

- continued noncompliance with the protocol or study visits,
- severe illness or disability during the study for non-study issues,
- pursuit of subsequent alternative treatment for the same condition, or
- development of intolerable side effects where continued follow-up becomes too burdensome.

In addition, a subject may also choose to exit the study at any time, but will be strongly encouraged to participate in the follow-up visits for safety reasons (continued monitoring of subject safety). Sites should make every effort to contact all subjects for study follow-up to encourage visit compliance. Sites should keep a log of dates of attempted contact and results. After 3 unsuccessful attempts at contact (e.g., by telephone or email) and sending 1 certified letter to solicit their visit compliance a subject may be considered lost to follow-up.

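### The long-term study excludes subjects re-treated on the treated side while saying that all treated subjects are included, and no planned analysis counts re-treatment as lost benefit

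*Protocol*

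**What the plan says.** **Who is followed.** LTF 12 gives the purpose as to "set the follow-up schedule for all IDE #G120246 subjects out to Year 5". LTF 14.3 says that all subjects of the original IDE "will be rolled into this PAS study at whatever stage of follow-up is coming due". LTF 15.5 says: "All ExAblate treated subjects who were treated under ET002 or ET002-CA will be included in this study". LTF 13.1.2 has one exclusion criterion: "Subjects who have had a subsequent intervention for ET on their treated side". None of the first three sections refers to it.

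**What happens on re-treatment.** Under pivotal protocol 4.2.2.3.2 and LTF 14.2, a subject who opts for an alternative tremor treatment other than a medication change leaves the study. "The last set of evaluations prior to alternative therapy is considered the last study visit", and "No analyses of post alternative treatment changes are planned". LTF 17.1 also lets the investigator withdraw such a subject. None of these three sections mentions side.

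**How missing visits are handled.** LTF 15.6 calls for both observed-data and last-observation-carried-forward (LOCF) results and does not say which leads. LTF 15.7 applies the pivotal SAP, on site assessor data only. SAP 7 and 7.2.2 use LOCF for the Month-12 secondary endpoint (SE2) in the ITT set and no imputation in the per-protocol set.

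**What is compared.** LTF 16 asks whether favourable composite scores, relative to baseline, will "be sustainable among the patients who have received the treatment". SAP 10.6.3 tests the Month-12 mean improvement against zero. SAP 10.6.4 plans by-visit descriptive statistics, graphs and baseline-to-visit tests within group.

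**The concern.** The Year 2-5 data exist to show whether the benefit lasts. A second intervention on the treated side is a plausible sign that it did not. Pivotal protocol 1.3.2.3 itself foresees re-treating patients whose tremor recurs. A study that removes subjects on that sign, or freezes their score just before it, is likely to describe the remaining cohort as more durable than the treated cohort was.

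The second strand concerns LTF 18, which describes Month-12 outcomes as little changed from Month 3. A test of Month 12 against zero cannot support that description, because it can be passed after most of the benefit has gone.

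**Working it through.** **1. The handling of a subject re-treated on the treated side**

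| Handling | Source | Effect on later visits |
|---|---|---|
| Excluded at LTF entry | LTF 13.1.2 | Contributes no Year 2-5 visit. SAP 5.2.1, which LTF 15.7 brings in, would keep the subject in the ITT set. No section resolves this. |
| Exits during follow-up, LOCF | LTF 14.2, 15.6; SAP 7, 7.2.2 for SE2 | The last score before re-treatment is carried. |
| Exits, observed data or per-protocol | LTF 15.6; SAP 7, 10.6.4 | Absent from later visits. |
| Worst-case imputation | SAP 10.6.6 | Repeats the Month-3 primary analysis only, and only if much is missing. |

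No row counts the event as loss of benefit. It can appear only in the discontinuation counts, visit accountability and dropout listing (SAP 10.1), or as a captured alternative treatment that follows a change in neurological status (pivotal protocol 6.3).

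**2. Size of the effect on the mean, as an illustration**

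The number re-treated, k, is not given. Assume n = 56, that each such subject carries the Month-3 mean, and that 0% is the value to use instead. The shift in the Month-12 mean is k × 46.9/56:

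- k = 1: 0.84 points
- k = 3: 2.5 points
- k = 6: 5.0 points

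These are not bounds. Improvement can be negative, in which case scoring 0% would raise the mean. A carried score can exceed 46.9%. If a Month-6 score exists, that score is carried and not the Month-3 one. Years 2-5 cannot be sized at all: if k of n subjects are dropped and the rest average M, scoring the dropped subjects as 0% lowers the mean by M × k/n, and none of the three is given.

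**3. The Month-12 result in LTF 18, reproduced**

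Inputs (ExAblate ITT, N = 56): Month 3 46.9% (95% CI 40.3 to 53.5); Month 12 39.6% (34.0 to 45.3), p < 0.001. With t(0.975, 55) = 2.004:

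- SD at Month 3 = (53.5 − 40.3)/2 ÷ 2.004 × √56 = 24.6
- SD at Month 12 = (45.3 − 34.0)/2 ÷ 2.004 × √56 = 21.1
- Month-12 t = 39.6 ÷ (21.1/√56) = 14.0, which agrees with p < 0.001
- Smallest mean significant against zero = 2.004 × 21.1/√56 = 5.65 points, and 5.65/46.9 = 12% of the Month-3 mean

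SE2 passes easily, but passing it says little about retention.

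**4. Month-3 to Month-12 change**

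Difference = 39.6 − 46.9 = −7.3 points; 39.6/46.9 = 84% of the Month-3 value. The within-subject correlation r is not reported. SD of the change = √(21.1² + 24.6² − 2r × 21.1 × 24.6); SE = SD/√56; CI = −7.3 ± 2.004 × SE.

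| r (assumed) | SD of change | SE | 95% CI |
|---|---|---|---|
| 0 | 32.4 | 4.34 | −16.0 to +1.4 |
| 0.3 | 27.2 | 3.64 | −14.6 to just below 0 |
| 0.5 | 23.1 | 3.08 | −13.5 to −1.1 |
| 0.8 | 14.9 | 1.98 | −11.3 to −3.3 |

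The interval excludes zero from r of about 0.30 (0.28 to 0.32 allowing for rounding of the printed figures). The other three rows in LTF 18 did not fall: posture 64.3 to 65.5, Part C 63.8 to 64.0, QUEST 43.2 to 47.1.

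**The case against.** **The conflict may be narrower than it looks.** An eligibility section normally qualifies a general statement about all subjects. LTF 14.3 and 15.5 enrol people at their next due visit, and someone already exited from the pivotal study has none. This stands in part. The clearest residual case is a treated-side intervention after the pivotal study ended and before LTF entry, and the documents do not say that anyone is in that position. It still leaves the Year 2-5 denominator undefined, and it does not reconcile one treated-side rule with two side-neutral ones.

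**A reader might infer that the plan is silent on re-treated subjects.** It is not. The exit sections fix the last usable visit, and the SAP gives LOCF for SE2. The gap is the analysis status of subjects excluded by 13.1.2 and of exited subjects' later visits in Years 2-5.

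**A reader might infer that the plan fails its own durability question, or gives no view of the change from Month 3 to Month 12.** Neither follows. The question in LTF 16 and the endpoint in pivotal protocol 2.2 are both framed against baseline, and SE2 matches them. By-visit means are planned, and the −7.3 comes from two printed means. Only the paired interval is missing.

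**The LTF is observational, without a hypothesis, and 0% is only one choice of value.** Both are true. They argue for a sensitivity analysis and against changing any confirmatory test.

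**Conclusion.** The concern holds in this form. The inclusion and exclusion statements conflict, the Year 2-5 denominator is undefined, and neither dropping subjects nor carrying their last score counts treated-side re-intervention as lost benefit. The likely direction is towards better-looking durability, on the assumption that re-intervention on the treated side usually reflects returning tremor. The amount is unknown and may be nil.

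Separately, describing outcomes as stable to Month 12 fits three of the four rows in LTF 18 but has no planned interval behind it for the composite, which fell by 7.3 points. Whether that fall is distinguishable from zero depends on an unreported correlation, with the dividing line near 0.3. Both scores come from the same subjects and share one baseline, so zero correlation is the least plausible case. The calculation also treats both means as coming from the same 56 subjects.

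A reader might infer that the pivotal efficacy result is in doubt. The documents do not support that: the Month-3 primary endpoint and the SE2 test against zero are unaffected. The point is worth fixing, with medium confidence because its size cannot be determined.

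**What to change.** 1. **LTF amendment: population.** Reconcile 13.1.2 with 12, 14.2, 14.3, 15.5 and 17.1. Which visit or exit rule applies is for the sponsor to settle. Whatever it is, define the Year 2-5 analysis set as all ExAblate-treated subjects, using data held up to re-intervention. LTF 15.6 already allows the earlier study data to be used.
2. **LTF amendment: reporting.** Record the side of any re-intervention, and report by visit the cumulative proportion re-treated on the treated side.
3. **LTF amendment: sensitivity analysis.** For Years 2-5, on the site assessor scores that LTF 15.7 requires, count treated-side re-intervention as loss of benefit from its date, for example as 0% improvement. Leave confirmatory SE2 as it is.
4. **Outside the LTF amendment.** As a supplementary pivotal-trial output, clearly labelled post hoc, report the paired Month-12 minus Month-3 change in the Core Lab composite with its 95% CI, in subjects observed at both visits (a carried Month-3 score gives zero change by construction). Otherwise, qualify the stability statement in LTF 18 for the composite.

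**Cost.** Six sections to align, one analysis-set sentence, one added field for side, and a few extra outputs from data already collected. No extra visit is needed. The downside is that durability figures may look less favourable, and that 0% is one value among several that could be defended.
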